PRoFLUID statistical analysis plan

The PRoFLUID investigators

Finalized on 21-09-2025

Methods

Design

PRoFLUID is an international prospective observational cohort study in critically ill invasively ventilated patients that receive ventilation for at least 24 hours. We expect a minimum of 200 ICUs from 30 countries to participate in this study. Patients in participating centers are screened on a daily basis. Eligible patients are included during a 28-day period, from Monday at 8:00 AM to the Monday 4 weeks later at 7:59 AM (in time zones of the participating centers).

Centers are expected to include 20 consecutive patients. After this, centers can either stop study inclusion or decide to enroll more patients. Centers that decide to continue enrollment will have to enroll the next 20 consecutive patients before they are given the option to stop study enrollment, until day 28.

Data regarding fluid administration, vasopressor use, diuretics use, oxygen exchange, and kidney function will be collected daily from the start of invasive ventilation. Collection will be retrospective, for the previous day. Clinical complications will be evaluated on day 90 after start of invasive ventilation, death or hospital discharge, whichever comes first.

Patients

Patients are eligible for participation in PRoFLUID if: (I) admitted to a participating ICU; (II) receiving invasive ventilation within three days of ICU admission; and (III) having received invasive ventilation for at least 24 hours. Patients younger than 16 years, and patients that are transferred under invasive ventilation from another ICU are excluded from participation in the study.

Primary outcome

The primary outcome is the provided fluid therapy in terms of volume per indication in the first 3 days after start of invasive mechanical ventilation, particularly the volumes of resuscitation fluid.

Secondary outcome

Secondary outcomes of this analysis consider the type of fluid used during the first 3 days after start of invasive mechanical; cumulative fluid balance over the first 7 days after start of invasive mechanical ventilation; the timing of start of diuretics or ultrafiltration . Additionally, secondary outcomes will include patient related outcomes such as mortality during ICU and hospital admission; ventilator free days at day 28; and duration of ventilation in survivors and non-survivors.

Stratification

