To adjust for case-mix differences across SOFA tertiles and investigate factors that influence fluid management, multivariate regression analysis will be performed, adjusting the administered fluid volumes for the following baseline variables: duration of first study day; sex; age; weight; and admission diagnosis. The differences in fluid administration between SOFA tertiles be evaluated.

Secondary endpoints may be described and differences in the distributions between SOFA tertiles regions may be tested using regression analysis or Kruskal-Wallis test. Associations between fluid balance and clinical outcomes will be assessed using Cox proportional hazards modelling with fluid balance as a time-dependent covariate. The model will be adjusted for duration of day 0, age, sex, weight, baseline SOFA, and admission diagnosis. Other covariates may also be considered for the model if deemed appropriate.

Sensitivity testing will be performed to assess the robustness of findings. All statistical analyses will be performed using R. We consider $p < 0.05$ to be statistically significant.

Table 1 – Minimal list of proposed tables and figures

	Description
Main paper	
Table 1	Baseline Characteristics
Table 2	Clinical outcomes
	Cumulative distribution of volumes per indication for fluid administration over the first 3 days after intubation:
Figure 1	A four panels figure showing: A) Cumulative distribution of volume of resuscitation fluid per stratifying variable; B) Cumulative distribution of volume of maintenance or replacement fluid per stratifying variable C) Cumulative distribution of volume of IV medication per stratifying variable; and D) Cumulative distribution of volume of cellular blood product transfusion per stratifying variable
	Fluid input, output and balance over first 7 days after intubation
Figure 2	A three panels figure of line plots with 95% CI showing: A) total volume of fluid volume input per admission day by stratification variable; B) total volume of fluid volume output per admission day by stratification variable; C) Daily fluid balance by stratification variable.
	Types of fluid prescribed

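### Kruskal-Wallis should be ruled out for comparing when diuretics or ultrafiltration begin across SOFA tertiles, because patients who never start, or who die or leave first, have no start time

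*SAP*

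**What the plan says.** The SAP's Secondary outcome section names, one after the other, "cumulative fluid balance over the first 7 days after start of invasive mechanical ventilation; the timing of start of diuretics or ultrafiltration". The second of these is the outcome at issue. It carries no observation window and no rule for a patient who never starts.

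The Analysis plan handles all secondary outcomes together. It says "Secondary endpoints may be described", and that "differences in the distributions between SOFA tertiles regions may be tested using regression analysis or Kruskal-Wallis test". No sentence gives the diuretic or ultrafiltration outcome a method of its own.

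The only time-to-event method in the SAP comes in the next sentence and serves another question: "Associations between fluid balance and clinical outcomes will be assessed using Cox proportional hazards modelling with fluid balance as a time-dependent covariate". The Design section says what ends observation for complications ("Clinical complications will be evaluated on day 90 after start of invasive ventilation, death or hospital discharge, whichever comes first") but not for this outcome. It also says "diuretics use, oxygen exchange, and kidney function will be collected daily from the start of invasive ventilation", so the start of diuretics is known to the day. Eligibility requires "having received invasive ventilation for at least 24 hours".

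**The concern.** Kruskal-Wallis ranks one observed value per patient. A patient who is never given a diuretic or ultrafiltration has no start time. Nor has a patient who dies or is discharged before a start. Two ways remain to run the test. One is to analyse starters only, which selects patients on the outcome. The other is to give non-starters a rank, which the SAP does not define and which treats death, discharge and never needing treatment as the same thing.

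The groups compared are severity tertiles, so equal rates of death and discharge cannot be presumed. If exit differs, start times among starters differ even when patients still under observation start at the same daily rate, because faster exit removes the late starters. A reader could then be told that sicker patients start earlier, or later, when only the time observed has changed. The SAP sets a 0.05 significance threshold, so such a result could be reported as significant.

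**Working it through.** The SAP gives no event rate, sample size or power for this outcome, so there is no planned figure to reproduce. The check asks what Kruskal-Wallis does when the start rate is identical in all tertiles.

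**Inputs from the SAP.** At least 200 ICUs with 20 patients each: 200 × 20 = 4,000, and 4,000 / 3 ≈ 1,333 per tertile. Threshold 0.05. No exit during the first day, in line with the 24-hour eligibility rule.

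**Assumptions.** Start hazard λ = 0.15 or 0.25 per day in every tertile. After day 1, exit hazard h per day, with death and discharge pooled. Window of 7 days.

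**Direct calculation.** The share started by day t (t ≥ 1) is

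F(t) = 1 − e^(−λ) + [λe^(−λ)/(λ+h)] × [1 − e^(−(λ+h)(t−1))].

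Take λ = 0.15, with h = 0.03 in the lowest and 0.12 in the highest tertile:

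- Lowest: F(7) = 0.1393 + (0.1291/0.18)(1 − e^(−1.08)) = 0.1393 + 0.7173 × 0.6604 = 0.613.
- Highest: F(7) = 0.1393 + (0.1291/0.27)(1 − e^(−1.62)) = 0.1393 + 0.4782 × 0.8021 = 0.523.
- Median among starters, from F(t) = F(7)/2: 2.47 vs 2.09 days. The highest tertile looks 0.38 day **earlier**.
- Median with never-starters ranked last, from F(t) = 0.5: 4.88 vs 6.20 days. The highest tertile looks 1.32 days **later**.

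The start hazard is the same in both groups; only the handling rule differs. If exit falls with SOFA instead, both signs flip.

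**Simulation.** 2,000 simulated studies per setting, 1,333 per tertile, both values of λ. Exit hazards run from the lowest to the highest tertile.

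| Exit hazards per day | Kruskal-Wallis, starters only | Kruskal-Wallis, never-starters last |
|---|---|---|
| Flat: 0.06 in all; 0.10/0.09/0.10 | 5-7% | 5-6% |
| Mild: 0.12/0.10/0.10; 0.08/0.09/0.11; 0.10/0.08/0.07 | 8-14% | 7-12% |
| Moderate: 0.05/0.07/0.10 or reversed | 26-32% | 19-28% |
| Steep: 0.03/0.06/0.12; 0.02/0.05/0.10; or either reversed | 66-78% | 51-76% |

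The cause-specific log-rank test (the score test of a Cox model on tertile, censoring at exit or day 7) rejects in 4-6% in every setting. Repeats with 600 studies per setting gave 8-15% (mild) and 64-81% (steep) for starters only, and 3-8% for the log-rank.

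**Sensitivity.** With start known only to the day, Kruskal-Wallis rejects in 4-6% (flat), 11-13% (mild) and 52-80% (steep). With a 3-day window the range is about 5-13% across repeats, with isolated values near 15% in one of them.

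**The opposite error.** A separate, smaller simulation (150 studies, exit hazard 0.10 in all tertiles, no protected first day, 1,300 per tertile) made the start hazards truly different: 0.05/0.10/0.15. Kruskal-Wallis on starters rejected in 65% and the log-rank in 100%. With 300 per tertile the figures were 20% and 100%. Dropping non-starters therefore also hides real differences.

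**The case against.** **The SAP does not prescribe Kruskal-Wallis here.** This stands. A reader might infer that the wrong test is mandated for this outcome. The sentence is permissive twice over and covers all secondary endpoints, some of which suit a rank test. Regression could mean Cox, and none of the proposed tables or figures names this outcome. The fault is an open choice that includes an unsuitable test.

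**Not every rejection is false.** This also stands in part. A reader might take every figure in the table as a false-positive rate. With never-starters last, the test responds to who starts as well as when, and in these settings the share who start really differs. With λ = 0.25, F(7) is 0.2212 + (0.1947/0.28)(1 − e^(−1.68)) = 79% at h = 0.03, and 0.2212 + (0.1947/0.37)(1 − e^(−2.22)) = 69% at h = 0.12. Start time among starters is likewise a legitimate conditional description. The error lies in reading either result as a difference in the rate of starting.

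**The size is assumed throughout.** True. If death rises and discharge falls with SOFA, pooled exit could be nearly flat and the problem nearly absent. The large figures need a four- to five-fold exit gradient over 7 days. The SAP gives no ground for expecting that, or for ruling it out.

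**The window may be in the protocol.** Possibly, so its absence from the SAP carries little weight alone. The choice of test and the treatment of non-starters are still matters for the SAP.

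**A wider reading.** A reader might extend the argument to 7-day cumulative balance, listed beside this outcome. That is a separate quantity. The sign and size of any distortion depend on the assumed daily profile, and Figure 2 already plans "Daily fluid balance by stratification variable". It is not part of this point.

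**Conclusion.** The point holds as a limited one: Kruskal-Wallis should be excluded for this outcome. Under equal start rates, 1,333 per tertile and a 7-day window, the starters-only test rejects in about 5% of studies when exit is equal across tertiles, about 8-15% when it differs mildly and 65-80% when it differs steeply. With a 3-day window the range is about 5-13%. Ranking never-starters last is no safe alternative without a stated rule and interpretation, since it can reverse the apparent direction.

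All start rates, exit rates and windows are assumptions, so the figures show what could happen and do not forecast this study. The outcome is secondary and its test optional; the primary outcome of fluid volumes over 3 days is unaffected.

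**What to change.** In the Analysis plan, take this outcome out of the general sentence on secondary endpoints and give it its own:

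- Show the cumulative incidence of first diuretic or ultrafiltration by SOFA tertile, with death and discharge as competing events.
- Compare tertiles with a cause-specific Cox model.
- State the horizon, and which discharge ends observation.
- State that Kruskal-Wallis is not used for this outcome.

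The two results should be read together. The curves show who starts within the horizon, and the Cox model shows the rate among those still at risk. At equal start rates the curves still separate when exit differs (79% vs 69% above), while the Cox comparison does not.

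The cost is SAP wording, one further model and a little more reporting. Diuretic use is already collected daily, and death and discharge are needed for the mortality outcomes. If exit proves similar across tertiles, the conclusion will hardly change.

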Outcomes will be analyzed across the entire cohort. Stratification will be performed over tertiles of total sequential organ failure score (SOFA) on day of intubation, specifically:

- Moderate: First tertile
- Severe: Second tertile
- Very severe: Third tertile

If SOFA components are missing at baseline, the missing values will be imputed by the mean of the patient's available component scores to calculate the total SOFA score. Patients without any data on baseline SOFA are excluded from the analysis.

Analysis plan

Descriptive statistics will be used to describe study population and fluid management parameters. Data are presented as numbers and percentages for categorical variables and as means (+/- SD) or median and interquartile range [IQR] according to distribution. Where appropriate, statistical uncertainty will be expressed by 95% confidence intervals.

We will describe the volume per indication for intravenous fluid therapy over the following indication categories:

- Resuscitation fluid
 - Prescribed in response to hemodynamic impairment or shock
 - Usually, isotonic crystalloids or colloids
 - At a rate of at least 166ml/h (1L/6 hours)
 - Usually much faster or as a bolus
- Maintenance or replacement fluid:

- Maintenance Fluids
 - Cover daily water and electrolyte needs
 - Up to 100 ml/h infusion rate.
- Replacement fluids
 - To address fluid losses
 - For example given for burns, dehydration, losses through drains, keto-acidosis
 - Can have faster (e.g. > 100ml/h) infusion rates
 - Are not given as bolus
- Unknown indication
 - Prescribed intravenous fluid therapy for which it is impossible to distinguish between resuscitation, maintenance or replacement

The volumes of intravenous fluid therapy per indication will also be examined in the context of all other fluids that are provided:

- Fluid as a carrier for intravenous medication
- Fluid to ensure catheter patency
- Cellular blood product transfusion
- Oral feeding
- Oral fluids
- Parenteral feeding

These volumes will be described as absolute mean volumes in mL with 95% confidence interval, as mean volumes per kilogram of body weight with 95% confidence interval, and relative to each other (as percentage of total).

Fluid volumes will be plotted using cumulative distribution plots that display fluid volumes over the first 3 days after intubation.

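### The Cox model updates fluid balance over time but names only baseline adjusters, so its hazard ratio can differ from 1 through changing severity even when fluid has no effect

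*SAP*

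**What the plan says.** The Analysis plan section of the SAP assesses associations between fluid balance and clinical outcomes by "Cox proportional hazards modelling with fluid balance as a time-dependent covariate". On adjustment it says: "The model will be adjusted for duration of day 0, age, sex, weight, baseline SOFA, and admission diagnosis". It then adds: "Other covariates may also be considered for the model if deemed appropriate". No further variable, and no criterion for choosing one, is given. Sensitivity testing is promised in the same section without content. The mortality result goes into eTable 5 of the supplement.

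Four other places bear on this model:

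- The indication categories define resuscitation fluid as "Prescribed in response to hemodynamic impairment or shock".
- The Design section says: "Data regarding fluid administration, vasopressor use, diuretics use, oxygen exchange, and kidney function will be collected daily from the start of invasive ventilation". It continues: "Collection will be retrospective, for the previous day".
- The Secondary outcome section uses "cumulative fluid balance over the first 7 days after start of invasive mechanical ventilation".
- Figure 2, panel C, in the list of tables and figures uses a daily version: "Daily fluid balance by stratification variable". The SAP does not say which of the two enters the Cox model, or with what lag.

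**The concern.** The exposure changes from day to day, but severity is held at its starting value. A patient who deteriorates on day 3 may be given or retain more fluid because of that deterioration, and is also more likely to die. Baseline SOFA does not capture this. The HR then picks up the prognosis of the deterioration as well as any role of fluid. The direction is not fixed: if sicker patients receive or retain more, the HR rises; if more is removed from them, it falls.

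A second route is conditional. If the balance of the current day is entered, a patient who dies partway through a day has a shortened record, which is compared with the full days of those still at risk. With a positive mean balance this pulls the HR below 1, and it needs no confounding. The SAP adjusts for the length of the first day, so it recognises that partial days distort volumes, but it is silent on the last day.

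At stake is how eTable 5 is read: an HR clearly above or below 1 could be taken as evidence on fluid balance when it reflects severity or record length.

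**Working it through.** The SAP gives no event count, power or HR for this model, so there is no stated figure to reproduce. The check is a simulation in which fluid has no effect on death.

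**Input from the SAP.** n = 200 ICUs × 20 patients = 4,000 (Design).

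**Assumed inputs, not in the SAP.**

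- Severity: S_t = 0.8·S_(t−1) + noise, SD 1.
- Daily balance: F_t = m + a·S_t + N(0,1) litres.
- Death: log hazard slope 0.7 per SD of current severity (exp(0.7) ≈ 2.0); 10% mortality over days 1 to 7.
- Models: complementary log-log with day indicators, baseline severity and the balance term; 200 runs.

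**Step 1: lagged balance, baseline severity only.** HR per litre (share of runs with p < 0.05):

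| a (L per SD) | Cumulative | Cumulative, plus severity on last balance day |
|---|---|---|
| −0.3 | 0.955 (44%) | 1.00 |
| 0 | 1.00 (7%) | 1.00 |
| 0.2 | 1.03 (20%) | 1.00 |
| 0.5 | 1.06 (76%) | 1.00 |

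The rejection rate in the last column is 7–8% throughout. For lagged daily balance at a = 0.5, baseline adjustment gives 1.175 (95%), adding severity on the balance day gives 1.00 (4%), and using severity from the day before instead leaves 1.085 (40%).

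**Step 2: hand check of the daily figure.** Given S_0, the variance of S_k is v_k = 1 − 0.64^k. For k = 0 to 6 this is 0, 0.360, 0.590, 0.738, 0.832, 0.893, 0.931, with sum 4.344. To first order, the slope of log hazard on lagged daily balance, pooled over days and weighted by the variance of balance, is

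0.7 × 0.8 × a × Σv / Σ(1 + a²v) = 0.28 × 4.344 / (7 + 0.25 × 4.344) = 1.216 / 8.086 = 0.150,

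so HR ≈ exp(0.150) = 1.16, close to the simulated 1.17. Once severity on the balance day is in the model, what remains of the balance is noise unrelated to death, which is why the HR returns to 1.

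**Step 3: a second specification.** With a Cox partial likelihood, a mean balance of 0.8 L falling by 0.15 L per day, and 60 runs, the lagged, baseline-adjusted HR at a = 0.5 was 1.054 (cumulative) and 1.149 (daily). Adding severity on the risk day itself, one day later than in step 1, gave 0.999 and 0.998.

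**Step 4: same-day balance with a partial death day.** The death-day balance is multiplied by a Uniform(0,1) fraction, so the mean shortfall with a = 0 is 0.5 × m: 0.35 L at m = 0.7 and 0.15 L at m = 0.3. With a = 0, cumulative HR was 0.93 (88%) and 0.97 (26%) respectively. In the second specification, a = 0 gave 0.953 cumulative and 0.833 daily. With a lag these became 0.998 and 0.999.

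**Step 5: limits of the remedy, lagged cumulative, a = 0.5.** With severity measured at reliability 0.7, the HR falls from 1.08 to 1.03 only, or to 1.05 with day-before severity. If fluid truly raises later severity (unconfounded HR 1.05), the severity-adjusted HR is 1.01: the effect is absorbed.

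**The case against.** Four objections have force.

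**The SAP claims only associations.** That wording appears in the Analysis plan and in eTable 5. An association adjusted for baseline need not equal 1 when fluid has no causal effect. This stands: the confounding route limits interpretation and is not an arithmetical error. It is a reason to keep the baseline-adjusted model under that label, but not to leave readers without a model that addresses later severity.

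**No stated lag does not mean same-day balance.** Data are collected for the previous day, so entering completed days is at least as natural a reading. A reader might infer that the planned HR will be distorted by the day of death. The SAP does not support that: same-day entry is one possible implementation, and the artefact disappears with a lag. A reader might also infer that the unstated form and death-day handling alone must move a null HR far in both directions. The low end of such a range depends on the assumed mean balance. For same-day daily balance at a = 0.5 with a cut-short death day, the HR is 0.82 at +0.7 L/day but 0.96 to 0.97 at +0.3 L/day.

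**The open clauses already permit the remedy.** Further covariates and sensitivity testing are allowed. They name no variable, timing or lag, so they commit to nothing before the data are seen.

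**Adjusting for daily severity is contestable.** It can absorb a mediated effect and leaves residual confounding (step 5). This stands, and is why it belongs in a sensitivity model with stated limits.

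Finally, it would be wrong to say that balance data end at day 7. Seven days is the window of one secondary outcome and of Figure 2; the SAP gives no end date for daily collection.

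**Conclusion.** The point holds at moderate weight. The stated model combines a time-updated exposure with baseline-only adjustment, although the SAP itself defines part of that exposure as a response to current shock and collects daily measures of severity. Even with lagged balance, the HR in eTable 5 can differ from 1 when fluid has no effect: illustratively about 1.06 per litre (cumulative) or 1.17 (daily) at 0.5 L per SD of severity, and below 1 if sicker patients have more fluid removed. These figures rest on the assumed persistence of severity, its link to death, 10% seven-day mortality and the noise in daily balance. They show that the bias is possible in either direction, not its size or sign in this cohort.

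The partial death day is a further risk only if same-day balance is used, and its size depends strongly on the mean daily balance. The primary outcome, a description of volumes by indication, is not affected.

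**What to change.** In the Analysis plan:

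1. Define the exposure as fluid balance up to the end of the previous day, and state whether it is daily or cumulative.
2. Keep the baseline-adjusted Cox model, presented as an association.
3. Prespecify beside it in eTable 5 a sensitivity model that adds the daily vasopressor, oxygenation and kidney values, taken from before or on the last balance day included. State which timing is used: with daily balance, day-before values left residual bias in the illustration.
4. State that this model may absorb an effect of fluid acting through later severity, and that it removes confounding only as far as severity is measured. A marginal structural Cox model is an optional addition.
5. If balance is collected only to day 7, state how it is carried afterwards.

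The cost is a few sentences and some code on data that the SAP already plans to collect. The lag gives up a little information from the current day, and the sensitivity model carries the absorption risk named in item 4.

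### The fluid balance Cox model names no ICU or country term, so its hazard ratio may mix within-ICU and between-ICU associations

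*SAP*

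**What the plan says.** The SAP's Design section begins: "PRoFLUID is an international prospective observational cohort study in critically ill invasively ventilated patients". On scale it says "We expect a minimum of 200 ICUs from 30 countries to participate in this study" and "Centers are expected to include 20 consecutive patients", with optional further blocks of 20 per centre. Fluid is not randomised.

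The Analysis plan specifies the outcome model: "Associations between fluid balance and clinical outcomes will be assessed using Cox proportional hazards modelling with fluid balance as a time-dependent covariate". Its adjustment set follows: "The model will be adjusted for duration of day 0, age, sex, weight, baseline SOFA, and admission diagnosis". Two openings are left: "Other covariates may also be considered for the model if deemed appropriate" and "Sensitivity testing will be performed to assess the robustness of findings". Neither names ICU, centre or country. The significance criterion is "We consider $p < 0.05$ to be statistically significant".

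The list of proposed tables and figures places the mortality result in eTable 5 of the online supplement. The SAP mentions no ICU or country stratum, fixed effect, random effect or frailty. The word regions does occur once in the Analysis plan, but in the sentence on testing secondary endpoints across SOFA tertiles. It adds nothing to the Cox model.

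**The concern.** A Cox model with one common baseline hazard compares each patient who dies with everyone still at risk on that day, in whichever ICU or country. Its coefficient therefore draws on two contrasts: patients with different balances in the same ICU, and ICUs with different usual balances. If ICUs that run more positive balances also have higher (or lower) mortality for reasons the six patient-level adjusters do not capture, the second contrast shifts the hazard ratio even when balance and death are unrelated inside every ICU.

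This is a matter of the point estimate. A cluster-robust standard error widens the interval around the same shifted value.

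What is at stake is the reading of eTable 5. It would show one hazard ratio, and the plan offers no way to tell which contrast produced it. Because the ICU term is left to later discretion, whether the result crosses the 5% threshold could also depend on a choice made after seeing the data.

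**Working it through.** The SAP states no event count, hazard ratio or power for this model, so there is no figure to reproduce. The check asks how far the pooled hazard ratio moves when balance has no effect within ICUs.

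**Inputs.** From the SAP: 200 ICUs × 20 patients = 4,000 (treating centre and ICU as the same unit); significance level 0.05, taken as two-sided because the SAP does not say. Assumed: mortality of 29 to 30%; balance SD 1.0 L within and 0.5 L between ICUs; residual ICU log-hazard SD s of 0.3 or 0.4, meaning what is left after the listed adjusters; correlation r between ICU mean balance and ICU log-hazard; no within-ICU effect and no within-ICU confounding; balance fixed in time, as a simplification.

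**Approximate size.** The pooled log hazard ratio per litre is about the slope of ICU log-hazard on total balance:

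r × s × 0.5 / (1.0² + 0.5²) = r × s × 0.5 / 1.25 = 0.4 × r × s.

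| r | s | 0.4 × r × s | HR by formula | HR simulated | p < 0.05 in |
|---|---|---|---|---|---|
| 0 | 0.3 | 0 | 1.000 | 1.000 | 5% |
| 0.1 | 0.3 | 0.012 | 1.012 | 1.012 | 8% |
| 0.3 | 0.3 | 0.036 | 1.037 | 1.035 | 28% |
| 0.3 | 0.4 | 0.048 | 1.049 | 1.050 | 48% |
| 0.5 | 0.3 | 0.060 | 1.062 | 1.060 | 60% |
| 0.5 | 0.4 | 0.080 | 1.083 | 1.082 | 83% |

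The first two rows rest on 300 simulated cohorts each, the others on 400. For the last four rows, the same data fitted with the baseline hazard stratified by ICU gave hazard ratios of 0.999 to 1.001 and rejection in 4 to 6%. The standard error rose from 0.026 to 0.030, a ratio of 0.030 / 0.026 = 1.15. With 8 patients per ICU the ratio is 1.21.

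**Time-dependent balance and robust standard errors.** A second simulation used daily balance on days 0 to 6, then carried forward; mortality of about 37%; an ICU share of balance variance of 0.10 or 0.20; s of 0.3 or 0.5; and 150 replicates per scenario. Hazard ratios are per SD of balance, and the true within-ICU value is 1.

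| r | Pooled HR | Rejection, naive SE | Rejection, cluster-robust SE |
|---|---|---|---|
| 0 | 0.998–1.001 | 5–10% | 2–7% |
| 0.3 | 1.029–1.062 | 21–63% | 19–58% |
| 0.5 | 1.047–1.114 | 44–97% | 42–95% |

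The robust standard error hardly changes the result once r is not zero. Stratified by ICU, the hazard ratio was 0.997 to 1.005 in all 12 scenarios. Rejection was 2 to 11% in single scenarios and about 5% on average, against a simulation error of about ±3.5 points per scenario.

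**What stratification does not remove.** Both simulations above exclude confounding within ICUs. Adding an unmeasured patient severity (assumed correlation 0.3 with within-ICU balance, log-hazard 0.4 per SD), with s = 0.3 and still no true effect of balance, gives:

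| r | Pooled HR | ICU-stratified HR |
|---|---|---|
| −0.3 | 1.059 | 1.123 |
| 0 | 1.095 | 1.123 |
| 0.1 | 1.107 | 1.121 |
| 0.3 | 1.135 | 1.123 |

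In three of these four cases the stratified estimate lies further from 1 than the pooled one. Stratification isolates the within-ICU association; it does not make that association causal.

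**The case against.** The strongest reply is that differing practice and differing mortality do not by themselves make ICU a confounder. The two must be correlated after adjustment for age, sex, weight, SOFA, diagnosis and length of day 0, and the SAP gives neither that correlation, nor the spread of ICU mortality, nor the ICU share of balance variance. At zero correlation the pooled hazard ratio is unbiased. This stands, so the bias is a possibility that the plan leaves open, and any size given for it must include the harmless end of the range.

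A second reply is that stratifying by ICU is a choice of estimand and need not bring the estimate closer to the truth, because confounding by severity within the ICU stays. This also stands. A reader might infer that the stratified hazard ratio of 1.00 in the simulations shows the fix to be unbiased in general; it shows this only where no within-ICU confounding was built in.

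A third reply is that the SAP allows other covariates and sensitivity testing, so an ICU term is not excluded. That is correct, and a reader who concludes that the SAP commits to a model without ICU goes too far. But neither opening names centre or country, so nothing about them is prespecified.

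Finally, the model serves a secondary association reported in a supplement, and the SAP claims neither a causal nor a within-ICU effect. This limits the consequence. It does not settle what the reported number would mean.

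**Conclusion.** The omission is real: the model as written names only patient-level adjusters for a non-randomised exposure across at least 200 ICUs in 30 countries. Its hazard ratio can mix within-ICU and between-ICU association, and robust standard errors do not separate them.

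Under the stated assumptions the distortion runs from none at zero correlation to 8% per litre at correlation 0.5 with the larger ICU mortality spread. A negative correlation would pull the estimate the other way. All of this rests on assumed quantities.

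A reader might infer that ICU is certainly a confounder here, or that eTable 5 is bound to show a false association. The document supports neither statement, since it contains nothing on the residual correlation. What it does support is that the plan should settle in advance how ICU enters this model. The change is advisable and does not touch the study's main result, because the primary outcome is a description of fluid volumes that does not use the model.

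**What to change.** Prespecify an ICU-aware Cox model beside the pooled one. Either of two forms serves:

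- stratify the baseline hazard by ICU, so that fluid balance is compared only among patients of the same ICU; or
- enter the ICU's mean balance and the patient's deviation from it as separate terms, with a shared ICU frailty, which reports both components.

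Show the chosen model next to the pooled model in eTable 5, labelled as the within-ICU association, and add a country-stratified model as a named sensitivity analysis. State in the SAP that confounding by severity among patients of the same ICU remains and that the stratified hazard ratio is not to be read as causal.

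The cost is small. Enrolment is organised by centre, so the ICU should be known for every patient, and the stratified form needs one extra model term. Its standard error is about 15% larger at 20 patients per ICU and about 21% larger at 8, and ICUs with no deaths contribute nothing to it.
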